### Other Safety Assessments

Physical and neurological examinations performed at Visit 1 of protocols 093-045 or 093-046 will apply to Visits 1 (Screening) of the present study.

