## 3. Study design

### 3.1. General Description

This study is a long-term, multicenter, open-label, safety extension study in male and female subjects (aged 16 to 70 years, inclusive) with partial onset seizures who have just completed, discontinued, or exited the 18-week treatment phase of Protocols 093-045 or 093-046. The initial study duration is 1-Year Open-Label Period with the option of continuing study drug treatment Post-1-Year Open-Label Period until a subject discontinues study, the study drug becomes clinically available in the subject's locale, or the sponsor terminates the study drug clinical development program.

This study will evaluate the safety and maintenance of effect of long-term eslicarbazepine acetate treatment at flexible doses in the range of 800 mg to 2400 mg once-a-day (QD) over a 1-Year Open-Label Period and a Post-1-Year Open-Label Period.

[figure not shown]

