### 3.2. Study Schematic

EOS=end of study; ET=early termination; M=month; V=visit.

\*Corresponds to Visit 9 in Protocols 093-045 and 093-046. \*\*1200 mg QD for subjects who had a dose reduction while participating in Protocols 093-045 or 093-046.

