## 5. Efficacy and Safety Variables

### 5.1. Schedule of Evaluations

Procedures	Visit 1/ SCN a	Visit 2	Visit 3	Visit 4	Visits 5 and 6	Visit 7	Post-1-year Visit 8 onwards	EOS/ET	Computer Systems c
	Day 0	Week 1	Mont h 1	Mont h 3	Months 6 and 9	Month 12	Month 15 onwards b		
Informed Consent	X								
Inclusion/Exclusion Criteria Review	X								A
Physical Examination	• d							X	A
Neurological Examination	•							X	A
Vital Sign Measurements	•	X	X	X	X	X	X	X	A
Height	•							X	A
Weight e	•	X	X	X	X	X	X	X	A
Clinical Laboratory Evaluation (Serum Chemistry, Hematology, and Urinalysis) f	•		X	X	X	X		X g,h	B
Coagulation Testing (PT/INR, PTT)	•		X	X	X	X		X g	B
Thyroid Panel (T 3 , T 4 , and TSH)	•		X	X	X	X		X g	B
Lipid Panel (total cholesterol, HDL-cholesterol, LDL-cholesterol, and triglycerides) f	•		X	X	X	X		X g,h	B
Bone Turnover Markers i	•				X h	X		X g	B
Serum Pregnancy Test k	•		X	X	X	X		X g	B
Urine Pregnancy Test k							X	X	
Urine Drug Screen (Central Lab)	•								B
12-Lead ECG	•		X	X	X	X		X h	C
MADRS	•				X j	X	X l	X	A
QOLIE-31 m	•				X j	X	X il	X	A
PGI Scale							X	X n	
C-SSRS o	•	X	X	X	X	X	X	X	A
Health Outcomes Assessments	•	X	X	X	X	X	X	X	A
Adverse Events	•	X	X	X	X	X	X	X	A
Concomitant Medications	•	X	X	X	X	X	X	X	A
Dispense Seizure Diary	X	X	X	X	X				
Document Seizures in Seizure Diary		X	X	X	X				A
Seizure Diary Review		X	X	X	X	X		X g	

Author:

Version Date: 19May2017

Copyright © 2010 Quintiles Transnational Corp. All rights reserved.

The contents of this document are confidential and proprietary to Quintiles Transnational Corp. Unauthorized use, disclosure or reproduction is strictly prohibited.

Procedures	Visit 1/ SCN a	Visit 2	Visit 3	Visit 4	Visits 5 and 6	Visit 7	Post-1-year Visit 8 onwards	EOS/ET	Computer Systems c
	Day 0	Week 1	Month 1	Month 3	Months 6 and 9	Month 12	Month 15 onwards b		
Dispense Study Drug	X	X	X	X	X	X p	X		A
Dispense Emergency Medication	X								
Drug Accountability		X	X	X	X	X	X	X	A
Dispense/Review MEC	X	X	X	X	X	X	X	X	

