Abbreviations: A=Electronic Data Capture (Inform); B=Laboratory Information Management System (LIMS); C=Core Lab Over-Read; C-SSRS=Columbia Suicidality Severity Rating Scale; EOS=End of Study; ET=Early Termination; MADRS=Montgomery-Asberg Depression Rating Scale; NTx=N-telopeptides of type I collagen cross-links; SCN=Screening; 25-OHD=25-hydroxyvitamin D; TSH=thyroid stimulating hormone; PGI=Patient Global Impression; PTH=parathyroid hormone; QOLIE-31=31-Item Quality of Life in Epilepsy.

- a. Demographic information, medical history, psychiatric history, medication history, magnetic resonance imaging/computerized tomography scans, electroencephalogram data, HLA-B\*1502 genotyping, and Hepatitis B/C screen results collected during the screening visit of Protocols 093-045 or 093-046 will apply for this study as well.
- b. Clinic visits to occur at intervals of 3 months during the post-1-year part.
- c. Letters in this column identify the computerized systems that will be used in this protocol (Appendix IX in protocol).
- d. The symbol “•” represents procedures performed at Visit 9 of Protocols 093-045 or 093-046, the results of which will apply to Visit 1 of the present study as well. These procedures do not have to be repeated.
- e. In street clothes without shoes and jacket/coat.
- f. Fasting labs.
- g. These assessments are not required to be performed if this visit falls in the post-1-year part of the study.
- h. If this visit falls in the post-1-year part of the study, this assessment may be performed only if clinically indicated (per Investigator judgement on a previously noted abnormality).
- i. Includes serum 25-OHD, PTH, osteocalcin, bone-specific alkaline phosphatase, and urinary NTx.
- j. At Visit 5 only.
- k. Every 6 months (i.e. Visits 7, 9, 11, 13, etc.).
- l. Only in subjects ≥18 years at time of signing informed consent in Protocols 093-045 or 093-046.
- m. Only for subjects who discontinue study during the post-1-year part of study.
- n. Fill out “since last visit” scale (Appendix VII in protocol).
- o. Only for subjects who discontinue study during the 1-year part of study.
- p. Only for subjects who continue into the post-1-year part of the study.

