**3. Relative change in seizure frequency from baseline**

Seizure frequency change from the baseline period will be evaluated by using SSF per 4 weeks (28 days). The baseline period is the period from Visit 1 to Visit 2 from Protocols 093-045 or 093-046.

The relative (%) change in SSF for any interval of interest (including baseline) will be calculated as:

$$\frac{(\text{SSF during the interval of interest}) - (\text{SSF during baseline period})}{\text{SSF during baseline period}} \times 100$$

Further the relative change from baseline will be categorized into:

- 100% Decrease
- ≥ 75% - < 100% Decrease
- ≥ 50% - < 75% Decrease
- 0% to < 50% Decrease
- > 0% to < 25% Increase
- ≥25% to <50% increase
- ≥50% to <100% increase
- ≥100 % increase

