### **Baseline**

Change in seizure related efficacy parameters will be calculated with reference to the baseline period defined as the baseline period (From Visit 1 to Visit 2) from protocol 093-045 and 093-046. The change in QOLIE, MADRS and safety parameters will be calculated with reference to the baseline as Day 0 (Visit 2) for protocol 093-045 and 093-046.

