#### **7.7.6 Physical and Neurological Examinations**

The physical and neurological examinations of subjects at beginning of the study and end of study will be summarized by presenting the number and percentage of subjects with normal and abnormal findings in each body area (skin/extremities, EENT, head/neck, etc.) for the ITT population.

Listing of physical examination findings and neurological examination findings will be provided.

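### SAP 5.3.2 takes the entry physical and neurological examinations from parent Visit 1, whereas the schedule in 5.1 takes them from parent Visit 9 (minor; one visit number to correct)

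*SAP*

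**What the plan says.** Two places in the SAP name the source of the physical and neurological examinations that stand for entry to this study.

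- **SAP 5.3.2**, in the paragraph on other safety assessments, has this sentence: "Physical and neurological examinations performed at Visit 1 of protocols 093-045 or 093-046 will apply to Visits 1 (Screening) of the present study".
- **SAP 5.1, Schedule of Evaluations:** the rows for physical examination and "Neurological Examination" each carry a bullet at Visit 1 and an X at EOS/ET, and nothing in between. Footnote d says the bullet "represents procedures performed at Visit 9 of Protocols 093-045 or 093-046, the results of which will apply to Visit 1 of the present study" and adds that these procedures need not be repeated.

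Three other places bear on the point. Footnote a to the schedule lists the items carried from the parent screening visit: demographics, histories, imaging, EEG, genotyping and hepatitis screen. A note under the schematic in SAP 3.2 reads "Corresponds to Visit 9 in Protocols 093-045 and 093-046". SAP 5.3.1 places the examinations at Visit 1 and at EOS/ET.

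SAP 7.7.6 is the analysis that uses them. It summarises the examinations at the beginning and end of the study by "presenting the number and percentage of subjects with normal and abnormal findings in each body area". It does not say which visit supplies the beginning.

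**The concern.** The start examination is carried over from a parent study, so the SAP has to say from which parent visit. It gives two answers, and they fall on opposite sides of the parent treatment phase. The examinations are done only at entry and at EOS/ET, so the choice of entry source determines the whole start-to-end comparison in 7.7.6.

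If a programmer follows 5.3.2, an abnormality that first appeared during the parent study is missing from the beginning-of-study count and present in the end-of-study count. It then looks like something that developed in the extension. An abnormality that resolved during the parent study would look like an improvement in the extension. Treatment-emergent adverse events, by contrast, are counted from the first dose in this protocol (SAP 5.3.2, Adverse Events), so the two displays would cover different periods.

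**Working it through.** The plan gives no figure to reproduce. The check sets the texts side by side and places the parent visits in time.

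**1. Which text is the outlier?**

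| Source | Parent visit for the entry examinations |
|---|---|
| 5.3.2, Other Safety Assessments | Visit 1 |
| 5.1, both examination rows, read with footnote d | Visit 9 |
| 5.1, footnote a (items from parent screening) | examinations not listed |
| 3.2, note under the schematic | refers to Visit 9 |
| 7.7.6 | not stated |

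The schematic itself is not shown, so the anchor of its note cannot be seen. That row is supporting evidence only. The other rows are enough: the schedule assigns the examinations to parent Visit 9 by an explicit symbol, and the list of parent screening items leaves them out.

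**2. Was the source changed on purpose?** SAP 4.2 lists one change from the protocol's planned analyses, and it concerns the post-1-year completion fraction. The amendment summaries mention no change to the source of these examinations. Nothing marks Visit 1 in 5.3.2 as deliberate.

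**3. Where does parent Visit 1 fall?** For seizure frequency, SAP 5.2.2 says: "The baseline period is the period from Visit 1 to Visit 2 from Protocols 093-045 or 093-046". SAP 6.1 places parent Visit 2 at Day 0. SAP 5.2.2 places parent Visit 6, the first monotherapy dose, at Week 8. SAP 6.5 gives 10 weeks of double-blind monotherapy. Then:

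- 8 weeks + 10 weeks = 18 weeks, which agrees with the 18-week treatment phase in SAP 3.1.

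That parent treatment starts at Visit 2 is inferred, but the sum supports it. Parent Visit 1 therefore lies before parent treatment.

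**4. How far before entry to this study?** Subjects are those "who have just completed, discontinued, or exited the 18-week treatment phase of Protocols 093-045 or 093-046".

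- Parent completer: gap = 18 weeks + length of the parent Visit 1 to Visit 2 period. That length is not given, so the gap is at least 18 weeks.
- Subject who left the parent treatment phase early: the gap can be shorter, but parent Visit 1 is still before treatment.

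**5. What reaches the output?** Under 5.3.2, the beginning-of-study counts in 7.7.6 describe subjects before parent treatment. Under 5.1, they describe subjects at parent Visit 9, whose results stand for entry to this study. How many counts would differ depends on how many examination findings changed between those two visits. The documents give no such rate, so no numerical effect can be calculated.

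**The case against.** The strongest reply is that the documents already settle the matter. The symbol definition in 5.1 is explicit, 5.3.2 reads like a one-digit slip, and a careful programmer would follow the schedule. That is likely, and it is why the point is minor. It still leaves a data-source rule that is wrong as written, in the section that defines the safety endpoints, while 7.7.6 does not resolve it.

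A second reply is that a pre-treatment reference would be in keeping with the rest of the plan. SAP 6.1 says that change in "safety parameters will be calculated with reference to the baseline as Day 0 (Visit 2") of the parent studies, so the laboratory, ECG, vital-sign and weight summaries include the parent treatment phase by design. This stands as a limit on the harm: a reader should not infer that any pre-treatment reference is an error in this SAP. It does not rescue the sentence in 5.3.2. That sentence names Visit 1, not the Visit 2 safety baseline. It also does not define a baseline for change. It says the results apply to Visit 1 of this study, which is the role footnote d gives to parent Visit 9.

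Two stronger readings are tempting.

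- **Shares of time as bias.** For a parent completer followed for 52 weeks, at least 18/(18 + 52) = 26% of the start-to-end interval would precede the extension. A reader might take this as the size of the bias. It is a share of calendar time, not of findings misclassified, and it falls as follow-up lengthens.
- **A deficient table in 7.7.6.** A reader might infer that separate start and end percentages, without a shift table, are a fault. The SAP plans shifts for laboratory values and C-SSRS ideation but not for ECG abnormalities, so it sets no general standard that 7.7.6 breaks. That is a matter of preference and separate from the visit conflict.

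**Conclusion.** The contradiction is real and lies within the current SAP. Section 5.3.2 is wrong as written, and parent Visit 9 is the source the rest of the plan supports.

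The consequence is conditional: it arises only if 5.3.2 is followed in programming. It is then confined to one descriptive table of normal and abnormal counts at two times, in which the plan calculates no change. These examinations are not among the safety variables named in SAP 7.7. The listings in 7.7.6 and the treatment-emergent adverse event tables in 7.7.1 would partly show new findings anyway. No efficacy result is touched. The size of the effect cannot be estimated from the documents.

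The conclusion rests on one inference, that parent treatment begins at Visit 2/Day 0, which the 8 + 10 = 18 week sum supports. Severity: minor.

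**What to change.** 1. In SAP 5.3.2, Other Safety Assessments, change the parent visit number from 1 to 9, so that the examinations performed at Visit 9 of protocols 093-045 or 093-046 apply to Visit 1 (Screening) of this study.
2. In SAP 7.7.6, add one sentence stating that the beginning-of-study examination is the one from parent Visit 9.

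The cost is one digit and one sentence. No new data, table or analysis is needed. No exception to the baseline rule in 6.1 is needed either, because that rule governs change from baseline and 7.7.6 calculates none. One consequence should be understood: abnormalities that arose during the parent study will count as present at the start, so the table describes the extension only.

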### Columbia-Suicide Severity Rating Scale (C-SSRS)

Occurrence of suicidal ideation is defined as having answered “yes” to at least one of the 5 suicidal ideation sub-categories (wish to be dead, non-specific active suicidal thoughts, active suicidal ideation with any methods [not plan] without intent to act,

active suicidal ideation with some intent to act [without specific plan], and active suicidal ideation with specific plan and intent) at any evaluation. Occurrence of suicidal behavior is defined as having answered “yes” to at least one of the 4 suicidal behavior sub-categories (actual attempt, interrupted attempt, aborted attempt, and preparatory acts or behavior) at any post baseline evaluation. Suicidal ideation is rated on a 6-point scale from 0=’No ideation present’ to 5=’Active ideation with plan and intent’. A score of 4 or 5 on this scale indicates serious suicidal ideation.

Suicidality is defined as having at least one occurrence of suicidal ideation or at least one occurrence of suicidal behavior during the assessment period.

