#### **7.7.8 Columbia-Suicide Severity Rating Scale (C-SSRS)**

Results from the C-SSRS assessments will be summarized by presenting the number and percentage of subjects with any suicidality, suicidal behavior and type of behavior, and any suicidal ideation and type of ideation.

Shifts in suicidal ideation from baseline to worst post-baseline result will be presented. Worsening ideation is reflected in shifts from lower to higher values.

C-SSRS will be summarized from Visit 1 until the End of Study or Early Termination Visit for the ITT population.

Listing of the C-SSRS assessments will also be presented.

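### The C-SSRS incidence starts from a Visit 1 result carried over from the parent study, and ideation, behavior and suicidality have no common, defined counting window

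*SAP*

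**What the plan says.** SAP Section 5.3.2 (C-SSRS) defines three outcomes.

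- **Ideation:** a yes on any of five sub-categories, the last phrase being "active suicidal ideation with specific plan and intent) at any evaluation".
- **Behavior:** a yes on any of four sub-categories, namely "actual attempt, interrupted attempt, aborted attempt, and preparatory acts or behavior) at any post baseline evaluation".
- **Suicidality:** "at least one occurrence of suicidal ideation or at least one occurrence of suicidal behavior during the assessment period". The SAP does not say what that period is.

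Three other places bear on which records are counted.

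- Section 7.7.8 sets the reporting window: "C-SSRS will be summarized from Visit 1 until the End of Study or Early Termination Visit for the ITT population". It adds one further display: "Shifts in suicidal ideation from baseline to worst post-baseline result will be presented".
- Section 6.1 (Baseline) says that change in "safety parameters will be calculated with reference to the baseline as Day 0 (Visit 2) for protocol 093-045 and 093-046". Section 7.7 lists the C-SSRS among the safety variables, but neither C-SSRS section names a baseline.
- In the Section 5.1 schedule, the Visit 1 cell for the C-SSRS holds a bullet. Footnote d explains that bulleted procedures were done at Visit 9 of the parent study, "the results of which will apply to Visit 1 of the present study as well".

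**The concern.** Two adjacent definitions carry different time limits, and a composite is built from them. A programmer who follows the words would apply two filters. One who reads the sections together might apply one. The SAP does not settle which is meant.

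A second problem does not depend on that choice. The incidence begins at Visit 1, and the C-SSRS recorded there belongs to the parent study. A subject whose only positive answer was at parent Visit 9 would appear in the 093-050 table as having had ideation during 093-050.

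Safety is the primary objective (Section 2.1) and suicidality is named in a secondary objective (Section 2.2). The study is an open-label extension with no comparator arm, so an upward error in the incidence is not offset by the same error in a control group.

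**Working it through.** The plan states no C-SSRS rate, and no sample-size or power calculation bears on this point, so there is no figure to reproduce. The check sets the sections side by side.

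**Step 1. Which evaluations count under each reading**

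| Reading | Ideation window | Behavior window | Do they differ? | Is the carried-over Visit 1 result counted? |
|---|---|---|---|---|
| (a) Section 5.3.2 taken literally, baseline = parent Visit 2 | All evaluations, parent baseline included | After parent Visit 2 | Yes, by the parent baseline record | Yes, for both |
| (b) Section 7.7.8 window, baseline = parent Visit 2 (Section 6.1) | Visit 1 onward | Visit 1 onward, all of it after parent Visit 2 | No | Yes, for both |
| (c) Section 7.7.8 window, baseline = extension Visit 1 | Visit 1 onward | After Visit 1 | Yes, by Visit 1 | Yes, for ideation only |

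The mismatch is present in (a) and (c) and absent in (b). The last column shows what is common to all three: the Visit 1 result enters the ideation count and therefore the composite.

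**Step 2. When the Visit 1 result was obtained**

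Footnote d makes it the parent Visit 9 assessment. The schedule first dispenses 093-050 study drug at Visit 1. The result therefore precedes the first open-label dose, although it follows the parent treatment phase.

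**Step 3. Comparison with the SAP's adverse event rule**

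Section 5.3.2 (Adverse Events) treats a dated event as treatment-emergent only if it occurs on or after the first study-drug dose in this protocol. Ideation dated to parent Visit 9 would fail that test as an adverse event, yet it would count in the C-SSRS table.

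**Step 4. Does the shift table repair this?**

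It covers ideation only and leaves the incidence and composite counts unchanged. It also depends on the unstated baseline. With parent Visit 2 as baseline, the Visit 1 result can itself be the worst post-baseline value. With Visit 1 as baseline, it cannot.

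**Step 5. Direction and size**

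Let *v* be the share of subjects with ideation at Visit 1, and *c* the share of those who report ideation again after the first open-label dose. Then

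incidence (Visit 1 onward) = incidence (after first dose) + *v*(1 − *c*).

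The added term is never negative. Neither *v* nor *c* is in the documents. For scale only, take the 348 subjects planned in Protocol Amendment 3 and these assumed values:

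- *v* = 0 or *c* = 1: excess 0
- *v* = 1%, *c* = 0.5: 0.01 × 0.5 = 0.5 points; 348 × 0.005 = 1.7 subjects
- *v* = 3%, *c* = 0.5: 0.03 × 0.5 = 1.5 points; 348 × 0.015 = 5.2 subjects
- *v* = 5%, *c* = 0: 5 points; 348 × 0.05 = 17.4 subjects

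For the composite, the excess is the share of subjects whose only counted ideation or behavior is at Visit 1.

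**The case against.** The strongest reply is that the SAP should be read as a whole. Section 7.7.8 starts the summaries at Visit 1 and Section 6.1 puts the safety baseline at parent Visit 2, so every summarized evaluation is already post-baseline and the two phrases select the same records. This stands as the most coherent reading. A reader might infer from Section 5.3.2 alone that ideation is certainly counted over a longer window than behavior. The documents do not support that. They do not exclude it either: the Section 6.1 sentence concerns change from baseline, and the C-SSRS sections do not refer to it.

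A reader might also infer that ideation from untreated subjects inflates the rate. That goes too far. Section 3.1 takes subjects from the 18-week treatment phase of the parent studies, so Visit 1 comes before open-label dosing but after parent-study treatment.

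It can further be said that the summaries are descriptive, that no planned analysis compares ideation with behavior, that the shift table lets a reader see earlier ideation, and that starting at Visit 1 may be deliberate. The first three are true and limit the consequence. The last is possible, but the SAP gives no reason for counting a parent-study result as an extension-study occurrence when its adverse event rule does the opposite.

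**Conclusion.** The point holds in a limited form. The wording of the windows is inconsistent, the composite's period is undefined and no C-SSRS-specific baseline is given. Whether ideation and behavior are in fact counted over different evaluations depends on the reading.

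What holds on every reading is that the Visit 1 result from the parent study feeds the ideation and suicidality incidence of 093-050. Under the parent Visit 2 baseline it feeds the behavior incidence too.

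The bias can only be upward. Its size cannot be found from the documents and may be zero. The 0 to 5 points shown in the working follow from assumed values and are not an estimate. A reader might be tempted to quote a particular overstated rate, but no C-SSRS rate in the documents would support one.

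**What to change.** In Sections 5.3.2 and 7.7.8:

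1. Count ideation, behavior and the suicidality composite over one window, namely evaluations after the first dose of study drug in 093-050, and define the composite's period as that window.
2. State which assessment is the C-SSRS baseline for the shift table.
3. Report the parent Day 0 and the carried-over Visit 1 results separately from the incidence, so that no information is lost.

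The cost is a wording change in two sections and one date filter in the programs. No new data are needed.

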### 2.2. Secondary objectives

- To evaluate the maintenance of the therapeutic effects of eslicarbazepine acetate over a 1-Year Open-Label Period and Post-1-Year Open-Label Period.
- To evaluate the health-related quality-of-life, suicidality, and depressive symptoms over a 1-Year Open-Label Period and Post-1-Year Open-Label Period.

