### 5.3. Safety Assessments and Endpoints

#### 5.3.1. Safety Assessments

Adverse events will be monitored throughout the study, starting at Visit 1.

Clinical laboratory tests to be collected include: serum chemistry, hematology, thyroid panel (free T3, free T4, and TSH), coagulation testing (prothrombin time [PT]/international normalized ration [INR] and partial thromboplastin time [PTT]), lipid panel (total cholesterol, high-density lipoprotein [HDL]-cholesterol, low-density lipoprotein [LDL]-cholesterol, and triglycerides), bone turnover markers (serum 25-hydroxyvitamin D [25-OHD], parathyroid hormone [PTH], osteocalcin, bone-specific alkaline phosphatase, and urinary N-telopeptides of type I collagen cross-links [NTx]), and urinalysis.

A 12-lead ECG collect ventricular heart rate, QT interval, P-R interval, QRS durations, R-R interval, and the QTc intervals corrected by Bazett (QTcB) and Fridericia (QTcF).

Vital signs include standing and supine systolic and diastolic blood pressure, standing and supine heart rate, respiration rate, weight, and body temperature.

Physical and neurological examinations will be conducted at Visit 1 and the End of Study or Early Termination Visit.

The C-SSRS is an instrument designed to systematically assess and track suicidal events (suicidal behavior and suicidal ideation) throughout the study. The C-SSRS includes the following four sections: Suicidal Ideation, Intensity of Ideation, Suicidal Behavior and Actual Suicide Attempts. The C-SSRS will be completed by the Investigator or Sub-Investigator (or qualified site personnel).

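### The SAP's C-SSRS definitions have no route for a death by suicide, so such a death can be missing from the suicidal-behavior and suicidality rates

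*SAP*

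**What the plan says.** Suicidality is part of a secondary objective in SAP Section 2.2: "To evaluate the health-related quality-of-life, suicidality, and depressive symptoms over a 1-Year Open-Label Period and Post-1-Year Open-Label Period".

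The C-SSRS paragraph of Section 5.3.2 sets the counting rules. Suicidal behavior requires a yes to "at least one of the 4 suicidal behavior sub-categories (actual attempt, interrupted attempt, aborted attempt, and preparatory acts or behavior", and that answer must be given "at any post baseline evaluation". The composite follows: "Suicidality is defined as having at least one occurrence of suicidal ideation or at least one occurrence of suicidal behavior during the assessment period".

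Section 5.3.1 describes the instrument: "The C-SSRS includes the following four sections: Suicidal Ideation, Intensity of Ideation, Suicidal Behavior and Actual Suicide Attempts". It also says who fills it in: "The C-SSRS will be completed by the Investigator or Sub-Investigator (or qualified site personnel". Section 7.7.8 then reports, from the C-SSRS assessments in the ITT population, the "number and percentage of subjects with any suicidality, suicidal behavior and type of behavior, and any suicidal ideation and type of ideation".

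Two further sections bear on a fatal event. Section 6.2 plans no imputation for safety measures. Section 7.7.1 tabulates serious adverse events and adverse events leading to death by system organ class and preferred term, for the 1-year, post-1-year and combined periods.

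**The concern.** The behavior list is closed and numbered, and each entry needs an answer at an evaluation. A subject who dies between visits attends no later visit, and the list has no entry for the death itself. The schedule in Section 5.1 leaves room for this: from Month 3 the visits are three months apart, and they stay so throughout the open-ended post-1-year period.

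At stake is the count in the only table that the SAP defines for suicidality. The study has a single arm and the summary is descriptive, so an omitted case is not balanced by a similar omission in a comparator. Any error runs one way, towards fewer events. Because such events are expected to be few, one case can decide whether the table shows zero or not.

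**Working it through.** The documents give no figure on this point to reproduce. The check is a reading of the rules, followed by simple arithmetic on size.

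**Step 1: is there any route for a suicide death into the C-SSRS rates?**

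- Section 5.3.2 (definition): four sub-categories, none of them completed suicide. The composite has no entry other than ideation or behavior.
- Section 5.3.1 (instrument): four sections are named, none of them for suicide death.
- Section 6.2 (missing data): no imputation for safety measures, so nothing is filled in after death.
- Section 7.7.8 (analysis): the source is C-SSRS assessments only.
- Section 7.7.1 (adverse events): the death is reported here, but no rule passes it to the C-SSRS summary.

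So no route is written down.

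**Step 2: how is a subject who dies by suicide counted under the literal rule?**

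| C-SSRS record | Suicidal behavior | Suicidality |
|---|---|---|
| Earlier post-baseline behavior yes, no form after death | Counted, for the earlier act | Counted |
| Earlier ideation yes within the assessment period, no behavior yes, no form after death | Not counted | Counted |
| No earlier yes, form completed after death with the fatal act entered as an actual attempt | Counted | Counted |
| No earlier yes, no form after death | Not counted | Not counted |

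The last row is lost from both rates and the second from the behavior rate. In the first two rows the fatal act itself does not appear under type of behavior. The third row depends on a site practice for which the SAP makes no provision.

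**Step 3: size.**

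Input: N = 348, the planned number after Protocol Amendment 3, which raised it from 270. This is an illustrative denominator. The ITT set in Section 7.1 is everyone who took open-label medication, and its size is not in the documents.

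Under-count in percentage points = 100 × (omitted cases) / N.

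- One omitted case, N = 348: reported 0/348 = 0.00%; with the case counted, 1/348 = 0.29%.
- Two omitted cases, N = 348: 0.00% against 2/348 = 0.57%.
- One omitted case, N = 270: 0.00% against 1/270 = 0.37%.
- No suicide: no difference.

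These figures assume that no other subject is counted. If others are, each omitted case still removes 100/N points from the rate concerned.

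**The case against.** The strongest reply is that the form is completed by site staff, not by the subject, and that an end-of-study or early-termination C-SSRS is scheduled. Staff could complete a form after the death and enter the fatal act as an actual attempt, a term that Section 5.3.2 does not restrict to non-fatal acts. This stands as a possibility. A reader might infer that a suicide is always left out, and the documents do not support that. They are silent, however, on completing a form after a death and on how to classify the act, so the count would rest on each site's habit.

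Second, the death is not hidden. It would appear by preferred term among serious adverse events and adverse events leading to death, in tables that serve the primary safety objective. This stands in full and limits the point to the C-SSRS rates. It also means that the two tables would not strictly contradict each other: Section 7.7.8 is labelled as C-SSRS results, and an instrument-based table may differ from an adverse-event table. Keeping it instrument-only is a defensible convention, but the SAP does not say that this is intended or warn the reader of it.

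Third, a reader might say that the worst outcome on the scale is scored as the best. The documents do not support this. The form is not reproduced in them, nothing shows that completed suicide is an item on it, and an earlier yes would still count the subject. Nor is suicidality a headline result: it is one of three topics in one secondary objective.

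Fourth, the effect is hypothetical and small. That is true of its expected size. It does not remove the case for settling the rule before any event is known.

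**Conclusion.** The point holds in limited form. Under the literal rule, a suicide between visits in a subject with no earlier yes and no later form is counted as no suicidal behavior and no suicidality. The stated definition would then give a wrong count for a named secondary objective, which is more than a missing detail.

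The size is about 0.29 percentage points per such case at N = 348, and zero without a suicide. This rests on three assumptions: the planned number approximates the ITT set, the subject had no earlier qualifying answer, and the site did not enter the fatal act as an actual attempt afterwards. The documents do not show whether any such case arose. The finding supports an inexpensive correction. It does not support a claim that suicide deaths would go unreported or that the safety conclusions are unsound.

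**What to change.** In the C-SSRS paragraph of Section 5.3.2, add that completed suicide counts as suicidal behavior, and therefore as suicidality, whether it is identified from adverse-event, serious-adverse-event or end-of-study data or from the C-SSRS, and even if no form was completed after the death. In Section 7.7.8, show it as a separate row under type of behavior, with a footnote giving its data source. State also that a subject with both an earlier qualifying answer and a completed suicide is counted once in each overall rate.

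The cost is a few lines of SAP text and one derived flag from adverse-event and death data already collected. There are two drawbacks. The table no longer reports the instrument alone, which is why the footnote is needed. And the rates can only stay the same or rise, which should be borne in mind when comparing them with C-SSRS rates from studies that did not count deaths this way.
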